5.1.2 Management of Patients Who Experience Specific Adverse Events

5.1.2.1 Management of Specific Adverse Events

Guidelines for management of specific adverse events are outlined in Table 5.

Table 5 Guidelines for Management of Patients Who Experience Specific Adverse Events

| Event | Action to be Taken ^a |
|---|---|
| 
Infection ^b Serious infection, opportunistic infection, or any infection requiring treatment with an IV antimicrobial agent Self-limited infections that require treatment
 | 
Discontinue study treatment and report event as an adverse event of special interest.
 
Withhold study treatment during antimicrobial therapy. Study treatment may resume after consultation with the Medical Monitor.
 |
| 
Bleeding
 | 
Bleeding events of moderate or greater severity are considered adverse events of special interest and should be reported to the Sponsor in an expedited manner.
 
For serious bleeding events or bleeding events requiring transfusion, radiologic endoscopic, or elective operative intervention, withhold study treatment and consult with the Medical Monitor.
 |
| 
Gastrointestinal effects Nausea, vomiting, and/or diarrhea
 | 
Manage according to site institutional guidelines.
 
Consider administration of study treatment with food as a possible mitigation strategy.
 |
| 
Malignancy Any malignancy
 | 
Discontinue study treatment, with the exception of non-serious local and resectable basal or squamous cell carcinoma of the skin. Report event as an adverse event of special interest to the Sponsor in an expedited manner.
 |
| 
Hepatotoxicity AST or ALT 3.0–5.0 × ULN AST or ALT > 3 × ULN in combination with a total bilirubin > 2 × ULN, of which at least 35% is direct bilirubin, or clinical jaundice
 | 
Withhold study treatment and consult with the Medical Monitor.
 
Discontinue study treatment. Report event(s) as adverse event of special interest (Hy’s law) to the Sponsor in an expedited manner.
 |

Table 5 Guidelines for Management of Patients Who Experience Specific Adverse Events (cont.)

| Event | Action to be Taken ^a |
|--|---|
| AST or ALT > 5 × ULN | Discontinue study treatment. Any elevation of an AST or ALT > 5 × ULN should be reported as an adverse event of special interest to the Sponsor in an expedited manner. |
| Cardiovascular effects | |
| Sustained (at least two ECG measurements > 30 minutes apart) QTcF that is > 500 ms or > 60 ms longer than the baseline value | Unless there is a clear alternative cause other than study drug, discontinue study treatment. ^c |
| Sustained absolute QTcF that is > 515 ms | Unless there is a clear alternative cause other than study drug, discontinue study treatment. ^c |
| An episode of torsades de pointes or a new ECG finding of clinical concern | Unless there is a clear alternative cause other than study drug, discontinue study treatment. ^c |
| Vascular inflammation | |
| Vasculitis | Discontinue study treatment and consult with the Medical Monitor. |

IV = intravenous; QTcF = QT interval corrected using Fridericia's formula; ULN = upper limit of normal.

Note: "Study treatment" includes study drug (fenebrutinib or placebo).

^a Any patient who discontinues study treatment should enter safety follow-up, if possible.

^b Appropriate laboratory investigations, including but not limited to cultures, should be performed to establish the etiology of any serious infection.

^c In rare circumstances, it may be acceptable to resume study drug, provided that any ECG abnormalities have resolved and that the patient is appropriately monitored. Clinical judgment should be applied.

5.1.2.2 Management of Increases in QT Interval

Study drug should be discontinued in patients who develop any of the following:

- Sustained (at least two ECG measurements > 30 minutes apart) QTcF that is > 500 ms or > 60 ms longer than the baseline value
- Sustained absolute QTcF that is > 515 ms
- An episode of torsades de pointes or a new ECG finding of clinical concern

Of note, if there is a new intraventricular conduction block, the increase in QRS complex duration should be subtracted from the QTcF change, because this represents an increase in QTcF unrelated to alterations in repolarization. Also of note, it is not uncommon to record arrhythmias, such as non-sustained ventricular tachycardia, supraventricular tachycardia, pauses, or atrial fibrillation, in healthy volunteers receiving placebo during periods of extended ECG monitoring. Therefore, it is critical that expert cardiology advice be sought to confirm any ECG changes and to ascertain the likelihood of a drug-induced arrhythmia versus the background occurrence of this arrhythmia. In such a situation, saving all available ECG data is highly suggested.

Management of patients with sustained QTcF prolongation should include close monitoring, with ECGs repeated at least hourly until two successive ECGs show resolution of the findings, correction of any electrolyte abnormalities, and possible discontinuation of other concomitant medications that are known to prolong the QT interval. Consultation with a cardiologist or electrophysiologist is recommended to help in the management of such patients.

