- Any major episode of infection requiring hospitalization or treatment with IV antimicrobials within 8 weeks prior to and during screening or treatment with oral antimicrobials within 2 weeks prior to and during screening
 - Antimicrobials include antifungal, antibacterial, and antiviral agents.
- History of or currently active primary or secondary immunodeficiency, including known history of HIV infection
- Evidence of chronic and/or active hepatitis B or C
 - Positive hepatitis B surface antigen (HBsAg) or hepatitis C serology (regardless of treatment status)
 - Positive hepatitis B core antibody (HBcAb)
- History of cancer, including hematologic malignancy and solid tumors, within 10 years before screening
 - Basal or squamous cell carcinoma of the skin that has been excised and is considered cured and in situ carcinoma of the cervix treated with apparent success by curative therapy > 1 year prior to screening are not exclusionary.
- Women who are pregnant, nursing (breastfeeding), or intending to become pregnant during the study or within 4 weeks after completion of the study
- For women of childbearing potential (including those who have had a tubal ligation): positive serum pregnancy test result at screening or on Day 1.
 - A serum pregnancy test is needed on Day 1 only if the urine pregnancy test is positive.
- History of alcohol, drug (e.g., tetrahydrocannabinol [THC], marijuana), or chemical abuse within the 12 months prior to screening as determined by the investigator
- Need for systemic anti-coagulation with warfarin, other oral or injectable anti-coagulants, or anti-platelet agents other than non-steroidal anti-inflammatory drugs (NSAIDs), aspirin, and other salicylates
- History of non-gallstone-related pancreatitis or chronic pancreatitis
- History of hospitalizations or transfusion for a GI bleed
- History of cerebrovascular accident (CVA) within 10 years or any history of hemorrhagic CVA
- History of spontaneous intracranial hemorrhage or history of traumatic intracranial hemorrhage within 10 years
- Known bleeding diathesis
- Screening 12-lead ECG that demonstrates clinically relevant abnormalities that may affect patient safety or interpretation of study results, including
 - QT interval corrected using Fridericia's formula (QTcF) >440 ms demonstrated by at least two ECGs > 30 minutes apart

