4.5.8 Electrocardiograms

A single ECG recording, without artifacts, must be obtained at specified timepoints, as indicated in [Appendix 1](#). The ECG intervals (e.g., PR, QRS, QT, QTcF, and RR) and heart rate from this ECG will be entered into the eCRF. Any morphologic waveform changes or other ECG abnormalities must be documented on the eCRF.

All ECG recordings must be performed using a standard high-quality, high-fidelity digital electrocardiograph machine equipped with computer-based interval measurements. Lead placement should be as consistent as possible. ECGs for each patient should be obtained from the same machine whenever possible. ECG recordings must be performed after the patient has been resting in a supine position for at least 10 minutes prior to beginning the ECG recording. All ECGs *can be performed without specific restrictions (e.g., can be performed at any time of day, before or after dosing, fasting or fed) but* are to be obtained prior to other procedures scheduled at that same time (e.g., vital sign measurements, blood draws). Body position should be consistently maintained for each ECG evaluation to prevent changes in heart rate. Circumstances that may induce changes in heart rate, including environmental distractions (e.g., television, radio, conversation) should be avoided during the pre-ECG resting period and during ECG recording.

For safety monitoring purposes, the investigator must review, sign, and date all ECG tracings. Paper copies of ECG tracings will be kept as part of the patient's permanent study file at the site. If considered appropriate by the Sponsor, ECGs may be analyzed retrospectively at a central laboratory.

If at a particular post-dose timepoint the mean QTcF is >500 ms or >60 ms longer than the baseline value, another ECG must be recorded, ideally within the next 5 minutes, and ECG monitoring should continue until QTcF has stabilized on two successive ECGs.

The Medical Monitor should be notified as soon as possible within 24 hours. Standard-of-care treatment may be instituted per the discretion of the investigator. If a PK sample is not scheduled for that timepoint, an unscheduled PK sample should be obtained. A decision on study drug discontinuation should be made, as described in Section 4.6.2. The investigator should also evaluate the patient for potential concurrent risk factors (e.g., electrolyte abnormalities, co-medications known to prolong the QT interval, severe bradycardia).

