5.1.1.7 Cardiovascular Effects

Fenebrutinib is considered to have a low potential to cause QT interval prolongation or to directly affect other cardiovascular parameters, at therapeutic exposures. A minimal increase in QTc (7 ms or 3%) interval was noted at 45 mg/kg in the single-dose cardiovascular safety pharmacology study in telemetry-instrumented dogs. [REDACTED]

[REDACTED] There have been no fenebrutinib-related changes in ECG parameters in the 4-week or 9-month dog toxicity studies.

Analysis of ECG data from the SAD and MAD studies in healthy subjects did not demonstrate any significant increase in either QRS interval or QTcF intervals. However, cardiac safety will be evaluated in all patients at baseline and throughout this study, with routine monitoring of vital signs (including heart rate and blood pressure), routine safety ECGs, and collection of adverse events (see Section [5.1.1.7](#) and Section [5.2.1](#)).

Management of patients with sustained QTcF prolongation (QTcF that is >500 ms or >60 ms longer than the baseline value) should include recording another ECG, ideally within the next 5 minutes, and ECG monitoring should continue until QTcF has stabilized on two successive ECGs. The Medical Monitor should be notified as soon as possible within 24 hours. Standard-of-care treatment may be instituted per the discretion of the

investigator. If a PK sample is not scheduled for that timepoint, an unscheduled PK sample should be obtained. A decision on study drug discontinuation should be made, as described in Section 4.6.2. The investigator should also evaluate the patient for potential concurrent risk factors (e.g., electrolyte abnormalities, co-medications known to prolong the QT interval, severe bradycardia).

Guidelines for management of study treatment in the event in the event of cardiovascular effects in patients are provided in Section 5.1.2. Please refer to the Fenebrutinib Investigator's Brochure for further details.

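### The QT stop rule differs between Section 5.1.2.2 and Table 5, Section 4.5.8 points to a section without the rule, and Appendix 5 lists two prohibited antihistamines as usable with caution

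*Combined protocol and SAP*

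**What the plan says.** **Stop rule.** Section 5.1.2.2 opens with "Study drug should be discontinued in patients who develop any of the following" and lists three criteria:

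- sustained QTcF above 500 ms or more than 60 ms over baseline;
- sustained QTcF above 515 ms;
- torsades de pointes or a new ECG finding of clinical concern.

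It states no exception and no route back to treatment. It does ask for a QRS adjustment when a new conduction block appears, and says "it is critical that expert cardiology advice be sought to confirm any ECG changes".

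Table 5 (Section 5.1.2.1) lists the same three criteria. The action in each row is "Unless there is a clear alternative cause other than study drug, discontinue study treatment". Footnote c adds that in rare circumstances "it may be acceptable to resume study drug, provided that any ECG abnormalities have resolved", with monitoring and clinical judgement.

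**Cross-reference.** Section 4.5.8 covers a QTcF above 500 ms or more than 60 ms over baseline and says "A decision on study drug discontinuation should be made, as described in Section 4.6.2". Section 5.1.1.7 repeats that sentence, but also says that guidelines on managing treatment after "cardiovascular effects in patients are provided in Section 5.1.2".

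**Drug list.** Section 4.1.2 excludes patients currently taking astemizole, terfenadine or ebastine. Section 4.4.3 restricts all three during the study, and Section 4.6.2 requires a stop for any medication prohibited under 4.4.3. Section 4.3.2.3 names seven allowed H1 antihistamines, and none of the three is among them. Appendix 5 nevertheless gives astemizole and terfenadine as examples in its row of CYP3A substrates that may be used with caution.

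**The concern.** A stop rule for a cardiac safety signal should give every site the same answer. Suppose a patient has sustained QTcF above the limit and also has low potassium. An investigator following Section 5.1.2.2 stops study drug. An investigator following Table 5 may treat the potassium as the clear other cause and continue dosing. Each has followed the protocol.

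The other two items send a reader to the wrong instruction. Someone working from the ECG section alone arrives at a list that does not mention QTcF. Someone checking a co-medication in Appendix 5, which is where Section 4.4.2.3 directs them for CYP3A substrates, finds two drugs shown as usable that other sections bar. What is at stake is consistent handling of a safety event. No efficacy estimate or error rate is involved.

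**Working it through.** No arithmetic applies beyond counting, so the check sets the current texts side by side.

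**1. The two stop rules**

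| Feature | Section 5.1.2.2 | Table 5 with footnote c |
|---|---|---|
| Criteria and thresholds | three | the same three |
| Default action | stop | stop |
| Exception for another clear cause | on 0 of 3 criteria | on 3 of 3 criteria |
| Resumption | not mentioned | rare cases, once the ECG has resolved |
| Input on cause | cardiology advice | clinical judgement (for resumption); no decision-maker named |

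The thresholds and the default agree, so the rules part only when a criterion is met and another cause is suspected. The cardiology advice and the QRS adjustment in Section 5.1.2.2 do not close that gap. They bear on confirming, attributing and measuring the event, and neither says that dosing may continue.

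Footnote c also names no consultation. Elsewhere in Table 5, resuming after a self-limited infection that needed treatment requires consultation with the Medical Monitor. For QT events, Sections 4.5.8 and 5.1.1.7 require that the Medical Monitor be notified within 24 hours, but do not give that person a part in the decision.

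**2. The cross-reference**

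Section 4.6.2 lists four mandatory reasons: pregnancy, malignancy, serious or IV-treated infection, and prohibited medication. The number that concern QTcF or ECG findings is 0 of 4. Its later wording leaves room for other reasons but supplies no QTcF criterion. From Section 5.1.1.7 the reader can still reach the rule through the pointer to 5.1.2. From Section 4.5.8 there is no such pointer.

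**3. The drug list**

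| Source | Astemizole | Terfenadine | Ebastine |
|---|---|---|---|
| 4.1.2 | excluded | excluded | excluded |
| 4.4.3 | restricted | restricted | restricted |
| 4.3.2.3 allowed list | absent | absent | absent |
| 4.6.2, through 4.4.3 | stop | stop | stop |
| Appendix 5 | caution | caution | not listed |

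Two of the three barred antihistamines therefore appear as usable with caution. The stop sentence in Section 4.4.3 is limited to use as CSU therapy, but Section 4.6.2 carries no such limit. Appendix 5 conflicts with the restriction on either reading.

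**4. The 515 ms criterion**

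"Sustained absolute QTcF that is > 515 ms" adds no patient to either rule. A value above 515 is also above 500, and the action attached is the same. This is redundant but harmless.

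**The case against.** The strongest reply is that the texts can be read together. Table 5 and Section 5.1.2.2 are adjacent, share thresholds, stop by default and expect a judgement of cause. Table 5 is titled as guidelines. Section 4.6.2 is not exhaustive and supplies the follow-up procedure after a stop. On the antihistamines, three specific provisions (4.1.2, 4.3.2.3 and 4.4.3) outweigh an examples column in an appendix. Much of this stands, and it is why the point is minor. It does not remove the conflict: one text permits continued dosing where the other does not, and a site should not have to work out which governs.

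Some stronger readings are tempting but not supported.

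- **That the exception is open-ended, so a co-medication raised by fenebrutinib could be blamed at will.** Table 5 does not define the term, but Sections 4.5.8 and 5.1.1.7 name what to evaluate: electrolyte abnormalities, QT-prolonging co-medications and severe bradycardia. Section 4.1.2 already excludes current use of well-known QT-prolonging drugs at doses with a meaningful effect, and Section 4.4.2.3 classes the CYP3A inhibition as mild. A new co-medication rule is not needed to settle this inconsistency.
- **That the conflict can be sized from baseline QTcF and the 440 ms entry limit.** Both texts use the same thresholds, so such a calculation only restates baseline plus 60 ms. The 440 ms figure is also a screening criterion needing two ECGs, not a cap on the baseline value.
- **That patients are exposed to a known QT hazard.** Sections 1.3.5 and 5.1.1.7 rate the QT potential as low at therapeutic exposures.

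Copying Table 5's exception into Section 5.1.2.2 would also make the two texts agree. It would, however, leave dosing open while the cause is still being judged.

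**Conclusion.** The point holds as three inconsistencies in current safety text: two versions of one stop rule that differ when another cause is suspected, one cross-reference that leads to a section without the rule, and one appendix row that contradicts the restriction on two drugs. Redaction and the amendment summary do not explain any of them. The conclusion rests only on reading the sections against each other.

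The size is small. Both rules stop by default, the causes to evaluate are named elsewhere, and several provisions already bar the two antihistamines. The documents give no basis for estimating how many patients would be handled differently. It is worth correcting because the instructions are operative and the correction is nearly free.

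**What to change.** Make the changes in one amendment.

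(a) Put one rule, in identical words, in Section 5.1.2.2 and Table 5. Suggested content: *When any listed criterion is met, stop study drug. Assess other causes (electrolyte abnormalities, QT-prolonging co-medications, severe bradycardia) with cardiology advice and the Medical Monitor. Resume only under footnote c, after the ECG abnormalities have resolved.* Keep the QRS adjustment. Removing the 515 ms line is optional.

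(b) In Sections 4.5.8 and 5.1.1.7, point the discontinuation decision to Section 5.1.2.2, and keep 4.6.2 as the reference for follow-up procedures.

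(c) Delete astemizole and terfenadine from the caution row of Appendix 5, or mark them there as prohibited under Section 4.4.3.

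The cost is wording in five places (5.1.2.2, Table 5 with its footnote, 4.5.8, 5.1.1.7 and Appendix 5), with no new assessments and no effect on sample size. Investigators lose a little discretion, and a patient whose QTcF rise has a clear non-drug cause would have dosing interrupted until the ECG resolves.

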5.2 SAFETY PARAMETERS AND DEFINITIONS

Safety assessments will consist of monitoring and recording adverse events, including serious adverse events and adverse events of special interest, performing protocol-specified safety laboratory assessments, measuring protocol-specified vital signs, and conducting other protocol-specified tests that are deemed critical to the safety evaluation of the study.

Certain types of events require immediate reporting to the Sponsor, as outlined in Section 5.4.

5.2.1 Adverse Events

According to the ICH guideline for Good Clinical Practice, an adverse event is any untoward medical occurrence in a clinical investigation subject administered a pharmaceutical product, regardless of causal attribution. An adverse event can therefore be any of the following:

- Any unfavorable and unintended sign (including an abnormal laboratory finding), symptom, or disease temporally associated with the use of a medicinal product, whether or not considered related to the medicinal product
- Any new disease or exacerbation of an existing disease (a worsening in the character, frequency, or severity of a known condition), except as described in Section 5.3.5.10
- Recurrence of an intermittent medical condition (e.g., headache) not present at baseline
- Any deterioration in a laboratory value or other clinical test (e.g., ECG, X-ray) that is associated with symptoms or leads to a change in study treatment or concomitant treatment or discontinuation from study drug
- Adverse events that are related to a protocol-mandated intervention, including those that occur prior to assignment of study treatment (e.g., screening invasive procedures such as biopsies)

5.2.2 Serious Adverse Events (Immediately Reportable to the Sponsor)

A serious adverse event is any adverse event that meets any of the following criteria:

- Is fatal (i.e., the adverse event actually causes or leads to death)

- Is life threatening (i.e., the adverse event, in the view of the investigator, places the patient at immediate risk of death)
 - This does not include any adverse event that had it occurred in a more severe form or was allowed to continue might have caused death.
- Requires or prolongs inpatient hospitalization (see Section 5.3.5.11)
- Results in persistent or significant disability/incapacity (i.e., the adverse event results in substantial disruption of the patient's ability to conduct normal life functions)
- Is a congenital anomaly/birth defect in a neonate/infant born to a mother exposed to study drug
- Is a significant medical event in the investigator's judgment (e.g., may jeopardize the patient or may require medical/surgical intervention to prevent one of the outcomes listed above)

The terms "severe" and "serious" are not synonymous. Severity refers to the intensity of an adverse event (e.g., rated as mild, moderate, or severe; see Section 5.3.3); the event itself may be of relatively minor medical significance (such as severe headache without any further findings).

Severity and seriousness need to be independently assessed for each adverse event recorded on the eCRF.

Serious adverse events are required to be reported by the investigator to the Sponsor immediately (i.e., no more than 24 hours after learning of the event; see Section 5.4.2 for reporting instructions).

